4.2 PRE-REGISTRATION EVALUATIONS

No specific laboratory tests or imaging tests results are required in order to guide the decision to enrol a patient in the study. The inclusion and exclusion criteria [as described below] are solely based on clinical assessment and history taking that would be available at the time of ICU admission.

4.3 INCLUSION CRITERIA

1. All adult comatose survivors after out of hospital cardiac arrest who are admitted to Derriford Hospital Intensive Care Unit [Penrose and Pencarrow wards]. The cause of cardiac arrest may be cardiac and/or non-cardiac or unknown at the time of enrolment.
2. All patients must be comatose before intubation [GCS equal or lower than 8].
3. All patients must be on one or more invasive organ support [e.g. Endotracheal intubation and mechanical ventilation, vasopressor and/or inotropic support, Continuous Renal Replacement Therapy Sedated and/or on neuromuscular blocking agents].
4. All patients must be sedated before and during the time of SSEP recording. If clinically indicated, neuromuscular blocking agents may also be used.
5. All patients must be on targeted temperature management as per Derriford ICU policy and protocol: For the first 24 hours after ICU admission, the target-temperature is 36°C with temperature control commencing within the first hour after critical care admission. For the

next 48 hours the temperature of the patients will be maintained between 36-37°C. The aforementioned temperature targets are achieved with external cooling devices.

6. Patients must have a CT scan of the head if severe cerebral pathology which is part of the exclusion criteria is clinically suspected.
7. Absence of all exclusion criteria

4.4 EXCLUSION CRITERIA

1. Non-comatose patients after ROSC
2. Coma secondary to Intracranial and Intracerebral haemorrhage
3. Patients with haemorrhagic shock
4. Patients with severe neurologic disability [CPC level higher than 2] during the pre-cardiac arrest period
5. Presence of active Demyelinating disease or past medical history of Demyelinating disease
6. Trauma-induced Cardiac arrest
7. Previously or during the current admission diagnosed Spinal Cord and /or brain stem lesions
8. Patients with Implantable defibrillator device [incompatibility with SSEP recordings device]

4.5 WITHDRAWAL CRITERIA

1. If during the analysis of the results will become evident that any of the exclusion criteria was present but not diagnosed during the time of enrolment
2. Decision of the patient-participant or their next of kin [who have initially consented] to withdraw from the study. All participants should be considered free to withdraw at any time from the study without giving reasons and without prejudicing further treatment
3. Patients that were lost during the follow up period
4. Patients that died within the first 24 hours
5. Patients that were transferred to other hospitals within the first 24 hours
6. Technical Error during recording of N20 and P25/30 SSEPs
7. Recordings of poor quality that it is not possible to be reliably interpreted

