After the SSEP recording the result of the N20 potential will be disclosed to the ICU clinical team as it happens currently as per the established Derriford ICU care and that will not be part of the study.

In the context of the research study:

For those patients who informed consent is obtained from their next of kins and are enrolled in the study, a copy of each recording will be produced for the study purposes by one member of the study team who is not participating in the interpretation of the recording. This copy will be anonymised by giving a specific number for the study. The date of the recording and the time will be available on the copy. The specific study number of each recording will correspond to the specific patient and will be kept on a list not accessible by the neurophysiology study team members who will perform the interpretation of the recording for the study purposes.

After each copy has been anonymised and added in the study databank, the anonymised copy will become available to the first and to the second interpreter [both members of the study team (neurophysiology)] who will interpret the recordings with regards to the presence and absence of the N20 and P25/30 SSEPs and they will record the results of their interpretation in the results databank. The two interpreters will be blinded for the personal and the clinical details of the patient. Also each one of the interpreters will not be aware about the result of the interpretation of the other. The ICU clinicians will not be aware about the results of the P25/30 interpretation as this will be part of the study and should not be disclosed to them during the conduction of the study. In this way, the P25/30 interpretation results will be impossible to affect the treatment of the patients and / or any of the clinical decisions made about them by the ICU clinicians who will strictly be kept unaware about the results of the P25/30 SSEPs.

In the unlikely event that there was a discrepancy in interpretation of the SSEP recording between the two delegated interpreters, then a third member [not a member of the study team] of the Neurophysiology team would be asked to review the anonymised recording only in order to decide about the result. The data of the patients as well as the date of recording and the results of the interpretation of the two study team interpreters would not be disclosed to the third independent interpreter.

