Interpretation of the SSEP recording for study purposes in details

Cortical N20 response is to be described as bilaterally absent (which is a good predictor of poor neurological outcome), or in other cases it may be present on one or both sides.

If the cortical N20 response is absent, the presence of the peripheral N9 and N13 response must be present to ensure that the response has arrived at the cortex. Cervical lesions need to be excluded if Cortical N20 response is absent.

The results of the SSEP from the patients enrolled to the study will be additionally interpreted for the presence or absence of the P25/30 waveforms. The additional interpretation for the study purposes will be as follows:

1. Check that baseline is clear and stable.
2. Check that all measured components are reproducible (should be possible to superimpose waves)
3. Check that peripheral nerve (N9) potential is present
4. Check that cervical spinal (N13) potential is present
5. Check that scalp (N20) potential is present and higher than 0.5 microvolts.
6. Check that scalp (P25/30) potential is present and higher than 0.5 microvolts..
7. As the P25/30 potential could be generated in the absence of N20 as they come from two distinct areas of the brain cortex, the presence of either the P25/30 or the N20 would be confirmed when the amplitude of each one is equal or higher than the amplitude threshold [0.5 microvolts] used for the analysis of the SSEPs. The presence and the amplitude of P25/30 will not be dependent on the presence of N20 in the same recording as each one of them can exist in the absence of the other
8. Measurement of the amplitude of recorded P25/30 and N20 and their combinations. Test if there is a correlation of the recorded amplitudes and their ratio [P25/30 to N20] with the positive predictive value of N20 for the favourable neurological outcome.

Explanation clarification between the usual Derriford ICU post cardiac arrest care and what additionally will be done for the research study purposes

[figure not shown]

Figure 3. Explanation-clarification of the usual Derriford ICU post cardiac arrest care and what additionally will be done for the research study purposes

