The study folder will contain four separate databanks: The first databank will contain the personal data of the patients [Name, Age, Hospital number, next of kin, and contact details] and their corresponding study numbers by which the patients will be known to all the members of the study team. During the conduction of the study, specific members of the study team will be responsible for the creation and management of this databank and only they will have access to this during the conduction of the study.

The second databank will contain all the clinical data that will be recorded for each patient [represented by a study number on this databank] on the day of ICU admission, the day of ICU discharge and the day of hospital discharge [see below for further information regarding clinical data expected to be collected for each patient].

The third databank will contain the results of the interpretation of the SSEP recordings with regards to P25/30 and N20 SSEPs. This databank will be accessible during the study conduction only by the study team members who will be the interpreters of the SSEP recording.

The fourth databank will contain the results of the neurologic outcome of the patients, in the form of Cerebral Performance Category recorded on ICU discharge day and on hospital discharge day.

At the End of the study, all data will be merged and statistically analysed and from the result of this analysis one or more relevant manuscripts must be submitted to a peer-review journal within the first 4 months after the completion of the study.

For each one of the patients-participants, the following clinical data must be collected prospectively, during the conduction of the study [at different stages i.e. at the time of enrolment and follow up] and must be kept safely in an anonymised form in a suitable database [see above for explanation]. The principles of patients' confidentiality and privacy must be applied at all times.

1. Age
2. Gender
3. Comorbidities [Scored by Charlson Comorbidity Index (see figure 3 on the Appendix)]
4. Pre-admission performance status [Assessed by the ECOG/WHO performance status score (see figure 2 on Appendix)]
5. Cardiac Arrest Rhythm [Rhythm that was initially recorded after cardiac arrest, usually at scene]
6. Bystander – witness of cardiac arrest and Cardiopulmonary resuscitation

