7. STATISTICS AND DATA ANALYSIS

7.1 DESCRIPTION OF STATISTICAL METHODS

Demographic information of participants will be summarized using descriptive statistics and presented in tables to provide an exploratory overview of the study population.

Continuous measures will be summarised as means, standard deviations and ranges where the distribution appears normal, and as medians, inter-quartile ranges and ranges otherwise.

Categorical data will be summarised by frequencies and percentages.

The primary outcome measure is the CPC score at hospital discharge with discrete values ranging from 1 to 5. The score will be dichotomised as 1-2 (positive or good outcome) and 3-5 (negative or poor outcome).

Sensitivity, specificity and predictive values of P25/30 in predicting poor outcome will be computed and the results compared to that of N20. Where appropriate, parameter estimates will be presented with 95% confidence intervals. Significant demographic and clinical predictors of poor neurological outcomes will be assessed and identified using regression models.

Statistical data analysis will be undertaken once data collection from the required number of participants is completed. No interim analysis is scheduled for this study.

Analyses will be performed in SPSS version 24 (or later), supplemented where required by Stata SE version 14.2 (or later) and R.

a. THE NUMBER OF PARTICIPANTS

Sample size calculation was based on diagnostic test accuracy (adequate sensitivity) of P25/30. A previous study (Kim et al. 2018) on patients treated by hypothermic targeted temperature management showed that the sensitivity of P25/30 in predicting poor outcome is 90.12% (95% CI, 81.5–95.6%). Though the proposed study will be based on those who are not treated by hypothermic targeted temperature management, the result (90%) is the 'best' available information regarding pre-determined sensitivity of P25/30. From experience of the team and analysis of the past three-years

pilot data, the prevalence of poor outcome was assumed to be 75%. In order the maximum marginal error of estimate does not exceed from 5% with 95% confidence level, and adjusting for drop-out/lack of consent at 3%, the minimum required sample size will be 115. No power was assumed in the calculation of the sample size as there is no testing of hypothesis.

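### Withdrawal criterion 1 allows removal for ineligibility during the analysis, after SSEP reads and outcomes are merged, with no blinding and no lock before the merge

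*Combined protocol and SAP*

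**What the plan says.** - **Removal rule.** Section 4.5, item 1, withdraws a participant "If during the analysis of the results will become evident that any of the exclusion criteria was present but not diagnosed" at enrolment.
- **Timing.** Section 7.1: "Statistical data analysis will be undertaken once data collection from the required number of participants is completed". Section 4.1: "At the End of the study, all data will be merged and statistically analysed". The third databank holds the SSEP reads and the fourth holds the CPC.
- **Exclusions that bear on the test.** Section 4.4, item 7, covers "Previously or during the current admission diagnosed Spinal Cord and /or brain stem lesions", and item 5 covers demyelinating disease. Section 4.2 says eligibility rests on information available at ICU admission, but item 7 admits lesions found later in the stay.
- **A check tied to the index test.** Section 4.1, in both the bedside and the study interpretation: "Cervical lesions need to be excluded if Cortical N20 response is absent". No matching requirement applies when N20 is present.
- **Blinding.** Section 4.1: "The two interpreters will be blinded for the personal and the clinical details of the patient". ICU clinicians do not learn the P25/30 result but are told the N20 result (Sections 4.1 and 5).
- **Analysis set.** Section 7.7 analyses all eligible participants, so a participant ruled ineligible late drops out of every estimate.

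**The concern.** In a prognostic accuracy study, who is in the analysis should be settled without knowledge of the index test or the outcome. Item 1 places the decision where both can be known. A lesion of the cord or brain stem, or demyelinating disease, can explain an absent cortical potential without severe cortical damage. A patient with an absent potential and a good recovery is therefore a natural candidate for a second look at eligibility, and the rule permits that look after the merge.

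The cervical-lesion requirement adds a separate route. It can bring a lesion to light in a patient with absent N20, while the same lesion in a patient with N20 present may go unsought.

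Specificity and positive predictive value are at stake. Both are named in the second primary objective (Section 2). The claimed strength of an absent potential is that it gives almost no false positives, so one or two removals can decide whether the result reads as perfect.

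**Working it through.** **1. Can results be seen when item 1 is applied?** Item 1 operates during the analysis. The analysis starts after data collection ends (Section 7.1), on merged data (Section 4.1). SSEP reads and CPC can therefore be side by side at that point. Who applies item 1 is not stated, so actual access is inferred from these three places.

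**2. Does any safeguard reach this step?** Interpreter blinding and the withholding of P25/30 from clinicians protect the reading and the care. Section 7.6 deals with deviations, but applying item 1 is following the plan. No section blinds the eligibility decision, dates it before the merge, or calls for an analysis with removed participants restored.

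**3. Which checks depend on N20?**

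| Check | Trigger | Depends on N20? |
|---|---|---|
| Cervical lesion | Absent N20 (4.1) | Yes |
| N9 and N13 potentials | Every study reading (4.1, steps 3 and 4) | No |
| CT of the head | Clinical suspicion (4.3, item 6) | No |
| Demyelinating disease, brain stem lesion | No search tied to N20 | No |

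The CT rule reads "Patients must have a CT scan of the head if severe cerebral pathology which is part of the exclusion criteria is clinically suspected". Only the first row is uneven by test result. It bears directly on N20, and on P25/30 only when both are absent, because Section 4.1 (step 7) treats the two potentials as independent. Item 1 itself can still remove any P25/30 false positive.

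**4. Direction.** Specificity = TN/(TN + FP). A check confined to test-positive patients never removes a TN, so each removal either raises specificity (an FP) or leaves it unchanged (a TP).

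**5. Size.** Inputs from Section 7, The number of participants: 115 patients, 3% loss, 75% poor outcome, sensitivity 90%. The number of false positives is my assumption (1 or 2).

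The stated 115 does not reproduce from its own inputs: 1.96² × 0.90 × 0.10 / 0.05² = 138.3; / 0.75 = 184.4; / 0.97 = 190.1, or 191. That is a separate matter. I use 115 here as the planned size.

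- Analysed: 115 × 0.97 = 111.6, about 112
- Good outcome: 111.6 × 0.25 = 27.9, about 28
- Poor outcome: 112 − 28 = 84
- True positives: 0.90 × 84 = 75.6, about 76

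| Assumed false positives | Specificity, kept (exact 95% CI) | Specificity, removed (exact 95% CI) | PPV, kept → removed |
|---|---|---|---|
| 1 | 27/28 = 96.4% (81.7 to 99.9) | 27/27 = 100% (87.2 to 100) | 76/77 = 98.7% → 100% |
| 2 | 26/28 = 92.9% (76.5 to 99.1) | 26/26 = 100% (86.8 to 100) | 76/78 = 97.4% → 100% |

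Each false positive is worth 1/28 = 3.6 points of specificity. With the 120 patients of Section 3 and no loss, there are 30 good outcomes and the figure is 1/30 = 3.3 points. Removing one true positive moves sensitivity from 76/84 = 90.5% to 75/83 = 90.4%.

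**The case against.** The other side has several good points.

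- **Removal can be legitimate.** Item 1 requires that an exclusion really was present. Most exclusions are matters of record, such as trauma, haemorrhage or an implanted defibrillator. This stands. The weakness lies in how and when ineligibility is detected and decided.
- **The cervical check is not driven by outcome.** It follows a recording usually made 24 to 36 hours after ROSC, before a discharge CPC exists, and it can remove true positives too. This stands. The trigger alone does not pick out false positives; that would take an outcome-driven search after the merge, which no section describes.
- **The false positives are hypothetical.** The protocol gives no rate of late-found lesions. The retrospective study in Section 1.1 reported a poor outcome in every patient with absent P25/30. The confidence intervals before and after removal overlap heavily, and the study is sized on sensitivity, which hardly moves. All true, so the size is an illustration and not a forecast.

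A reader might infer three stronger things. First, that the whole lesion search depends on N20: the table above shows that only the cervical check does. Second, that the person deciding will have the results in view: the protocol does not say who decides. Third, that specificity will be inflated: the documents show only that the rule permits it.

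None of this supplies a blinded or dated eligibility decision.

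**Conclusion.** The point holds as a stated rule that is open to bias. Item 1 schedules eligibility removals for the analysis stage, and nothing blinds them or completes them before the merge. For N20, detection of one kind of lesion can also differ by test result. For P25/30 that route applies only when both potentials are absent, but item 1 can remove any P25/30 false positive.

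At the planned size, one removal is worth about 3.6 points of specificity and can turn 96.4% into 100%. This rests on 28 good-outcome patients, on one assumed false positive, and on the inference that results are visible when item 1 is applied. Whether any such removal would occur cannot be judged from the documents. It should be fixed, as a cheap improvement, and before the databanks are merged, because a blinded check cannot be recovered afterwards.

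**What to change.** Replace item 1 of Section 4.5 with a rule to this effect:

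- The eligibility of every participant is re-checked from information already recorded. No additional tests are done, in line with Section 4.1.
- An existing team member makes the check, preferably one not involved in that patient's care, because treating clinicians are told the N20 result. The check uses an extract without SSEP results, CPC, death or length-of-stay data. An extract is needed because the list of clinical data in Section 4.1 includes CPC, date of death and length of stay.
- The same record review applies whatever the N20 result. Decisions are dated and locked before the databanks are merged.
- Every participant removed for ineligibility is listed with the reason, SSEP result and CPC.
- The accuracy estimates are repeated with all removed participants who have an interpretable SSEP and a CPC put back in.
- Ineligibility found after the merge is handled only in a sensitivity analysis.

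A uniform record review cannot undo uneven lesion-finding in usual care. The listing and the repeated estimates are there to show its effect.

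The cost is protocol wording, one data extract, a listing and one additional table. The downside is that a few patients found ineligible late stay in the main analysis, so specificity may be slightly less favourable.

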According to the Targeted Temperature Management protocol of the Derriford ICU, the body temperature will be maintained at 36°C for the first 24 hours and between 36-37°C for the next 48 hours up to a total of 72 hours. As per ICU management practice, organ support as required [mechanical ventilation, cardiovascular support, renal replacement therapy], continuous invasive and non-invasive multimodal monitoring [vital signs, respiratory and haemodynamic monitoring, neurologic monitoring] and treatment of the underlying cause of cardiac arrest [if known-diagnosed] will be provided. The targeted temperature management is achieved with the use of external cooling devices.

Between the 24 hours and the 36 hours after ROSC, the usual SSEP recording will take place in ICU by members of the neurophysiology team. The recording will be performed, as usual and normal ICU care without any modification for the study, while patients are on sedation [as described above]. The use of neuromuscular blocking agents will be applicable if indicated for any of the aforementioned clinical reasons or in order to achieve the best recording quality [clear recording of SSEP baseline in patients to facilitate the optimal interpretation of the recording mainly in patients with tremor or myoclonus] if that is not possible to be achieved while patients are on sedation. A single dose of Atracurium or Rocuronium will be administered for this purpose only if this is absolutely necessary. The Neurophysiology team members may request the use of neuromuscular blocking agent if they

think that the quality of their recording is poor. It will be the decision of the ICU consultant in charge if the neuromuscular blocking agent could be administered.

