	Channel 4	Fz/lps/ContErb – Erbs Ips/Cont

Sweep time: 100ms

Recording procedure

SSEPs must be recorded after at least 24hours following ROSC. Usually to be performed between 24-36 hours after ROSC.

Temperature must be recorded; mild to moderate hypothermia $\geq 36^{\circ}\text{C}$ does not abolish the cortical N20 responses. Cortical responses have been proven to remain until a nasopharyngeal temp of 20°C is reached.

The N20 remains present even at a sedation level sufficient to induce an iso-electric EEG.

Running the test

The established, used for many years in Derriford ICU, SSEP recording protocol is used. No changes in terms of either the method of recording or the length of the test would be done as a result of the study. Besides, the study does not have to do anything with the SSEP recording but with the further interpretation only of the recording paper for evidence of other potentials that could be used for prognosis.

The patient is positioned to reduce muscle artefact. If this is not possible and muscle artefact is high muscle relaxants may need to be prescribed to improve quality of recording and quality of SEP, especially in cases where it is thought to be absent.

The level of stimulation is subjective and needs to elicit a visible twitch of the appropriate muscle. Therefore this should be achieved prior to administration of muscle relaxant

Averaging begins once adequate stimulation is achieved, a minimum of 500 trials is required, and this must be increased where necessary. A minimum of two trials must be recorded to check for reproducibility.

Interpretation of the recording regarding N20s at the bedside for clinical purposes. This is part of the current established normal ICU care and is not part of the study.

Cortical N20 response is to be described as bilaterally absent (which is a good predictor of poor neurological outcome), or in other cases in may be present on one or both sides.

If the cortical N20 response is absent, the presence of the peripheral N9 and N13 response must be present to ensure that the response has arrived at the cortex. Cervical lesions need to be excluded if Cortical N20 response is absent. Immediately after SSEP recording, each recording will be interpreted for N20 and the result will be disclosed to the ICU clinicians as currently happens in the context of the ICU clinical policy and the Resuscitation Council UK Guidelines.

After SSEP recording

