7.3 THE LEVEL OF STATISTICAL SIGNIFICANCE

Whenever applicable, a 5% level of significance will be used.

7.4 CRITERIA FOR THE TERMINATION OF THE TRIAL.

As this is not an interventional study, the chance to terminate the trial is minimal.

7.5 PROCEDURE FOR ACCOUNTING FOR MISSING, UNUSED, AND SPURIOUS DATA.

Spurious and/or missing data will be summarised and reasons for missingness given where possible. All data analyses will be based on the complete data only.

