7.7 INCLUSION IN ANALYSIS

All eligible participants will be included in the analyses.

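### Withdrawing patients with failed or unreadable recordings leaves sensitivity and NPV estimated in readable recordings only, with no all-recorded estimate planned

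*Combined protocol and SAP*

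**What the plan says.** Section 4.5 (withdrawal criteria) includes, as item 6, "Technical Error during recording of N20 and P25/30 SSEPs" and, as item 7, "Recordings of poor quality that it is not possible to be reliably interpreted". Both act after enrolment. Section 4.1 gives the readers a checklist (clear baseline, reproducible components, N9 and N13 present, 0.5 microvolts for each cortical potential) but does not say when a recording becomes uninterpretable. The third reader is called only when the first two disagree.

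Section 7.1 states: "Sensitivity, specificity and predictive values of P25/30 in predicting poor outcome will be computed". It adds a comparison with N20, but no rule for an indeterminate recording and no supplementary analysis. Section 7.5 promises "Spurious and/or missing data will be summarised and reasons for missingness given where possible" and then rules: "All data analyses will be based on the complete data only". Section 7.7 says "All eligible participants will be included in the analyses" and does not mention section 4.5.

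Section 4.1 anticipates some difficult traces. A muscle relaxant may be given "to facilitate the optimal interpretation of the recording mainly in patients with tremor or myoclonus". Under the heading on running the test, better recording quality is said to matter "especially in cases where it is thought to be absent".

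**The concern.** Absence of P25/30 is the test result that predicts poor outcome. A patient whose trace cannot be read has had the test and received no answer. Withdrawing that patient takes a case out of the denominator of sensitivity, so the published figure answers a narrower question than it appears to: how often poor outcome is detected given that the recording could be read.

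This touches measures the study depends on. Sensitivity drives the sample size, and secondary objective 2 names sensitivity and NPV as the grounds on which P25/30 might beat N20. Secondary objective 3 promises evidence on the accuracy and reproducibility of the recording itself, and the frequency of failure is part of that evidence. The 3% allowance in the sample size names drop-out and lack of consent, not unreadable recordings.

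**Working it through.** **Inputs.** Section 7.1: expected sensitivity 90%, prevalence of poor outcome 75%, margin 5 points at 95% confidence, 3% attrition, N = 115. Specificity is set at 100% for illustration, because section 1.1 reports that in the cited retrospective study all patients with absent P25/30 had a poor outcome. The unreadable share u is not in the documents; 3%, 5% and 10% are assumptions.

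**Step 1: the plan's own figure.** The usual precision formula gives 1.96² × 0.90 × 0.10 / 0.05² = 138.3 poor-outcome patients; 138.3 / 0.75 = 184.4; 184.4 / 0.97 = 190.1, so 191. The stated 115 is not reproduced. It yields 115 × 0.97 × 0.75 = 83.7 poor-outcome patients and a half-width of 1.96 × √(0.09 / 83.7) = 6.4 points. That is a separate matter. The accuracy results below do not depend on it.

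**Step 2: which measures move.** Let TP, FN, TN and FP be counts in readable recordings, and Up and Ug the unreadable recordings with poor and good outcome. If unreadable counts as not positive, then over all recorded patients:

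- sensitivity = TP / (TP + FN + Up), which falls as soon as Up exceeds zero;
- specificity = (TN + Ug) / (TN + FP + Ug), which cannot fall;
- PPV = TP / (TP + FP), which is unchanged;
- NPV = (TN + Ug) / (TN + Ug + FN + Up), which falls unless the good-outcome share among unreadable recordings is at least the readable-only NPV.

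**Step 3: size with equal failure in both outcome groups.** Readable-only NPV is 0.25 / (0.25 + 0.75 × 0.10) = 76.9%. With unreadable as not positive, sensitivity = 0.90 × (1 − u) and NPV = 0.25 / (0.25 + 0.75 × (1 − sensitivity)). With unreadable as positive (absent), sensitivity = 0.90 × (1 − u) + u and specificity = 1 − u.

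| u | Not positive: sensitivity | Not positive: NPV | Positive: sensitivity | Positive: specificity | Positive: PPV | Positive: NPV |
|---|---|---|---|---|---|---|
| 0% | 90.0% | 76.9% | 90.0% | 100% | 100% | 76.9% |
| 3% | 87.3% | 72.4% | 90.3% | 97% | 98.9% | 76.9% |
| 5% | 85.5% | 69.7% | 90.5% | 95% | 98.2% | 76.9% |
| 10% | 81.0% | 63.7% | 91.0% | 90% | 96.5% | 76.9% |

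In the not-positive columns specificity and PPV stay at 100%. Under the opposite convention the pattern reverses: readable-only analysis then overstates specificity and PPV and slightly understates sensitivity.

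**Step 4: if failure is unequal.** With 5% of all recordings unreadable and every one in the poor-outcome group, the share lost there is 0.05 / 0.75 = 6.7%, and sensitivity (not positive) is 0.90 × (1 − 0.067) = 84.0%. At 10% it is 0.90 × (1 − 0.133) = 78.0%. If every unreadable recording had a good outcome, sensitivity would stay at 90%.

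**Step 5: precision.** Starting from 83.7 poor-outcome patients, 5% or 10% unreadable leaves 79.5 or 75.3, and the half-width moves from 6.4 to 6.6 or 6.8 points. The loss of precision is small; what matters is which patients the estimate describes.

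**The case against.** Accuracy among interpretable recordings is a legitimate quantity, and the title and objectives speak of recorded potentials. That stands: the readable-only figure should stay, labelled as such.

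Section 7.5 promises a summary of missing data with reasons, so the number of failures should come out. That stands in part. A summary gives neither a breakdown by outcome nor an estimate over all recorded patients.

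The protocol takes steps to avoid bad traces (muscle relaxant where needed, at least 500 sweeps, two runs), and the readers are blinded to clinical details. Failures may be few or none, and selection driven by outcome is less likely. That stands, and it is why the size cannot be fixed in advance.

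No passage says that an unreadable trace should be read as P25/30 present, so the NPV shift in particular depends on a convention brought from outside. That also stands, and it is the reason to show both bounds. Counting unreadable good-outcome patients as not positive also raises specificity if it is below 100%: with 90% in readable traces and 5% unreadable, it becomes 1 − 0.10 × 0.95 = 90.5%.

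Finally, a technical error is a failed measurement, and nothing in the documents suggests that it relates to outcome. It should be counted apart from uninterpretable traces.

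**Conclusion.** The point holds for sensitivity and NPV. As written, the plan estimates both only in patients with readable recordings, and nothing puts the others back. Taking unreadable as no prediction of poor outcome, with equal failure in both groups, the overstatement of sensitivity is 2.7, 4.5 or 9.0 points at an assumed 3%, 5% or 10% unreadable. It is zero if no recording fails. The plan's 5-point margin gives a sense of scale, but that margin is sampling error and this is a difference in definition.

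Four stronger readings might be inferred, and the documents do not support them:

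- That accuracy in general is overstated. Under this convention specificity and PPV are not.
- That the loss is known to be non-random. Section 4.1 ties difficult traces to tremor or myoclonus, and section 1.1 lists myoclonus among uncertain prognostic signs, so a link with outcome is plausible. No passage shows that unreadable traces remain after the quality steps or cluster by outcome. The sensitivity gap does not need such a link.
- That the comparison of P25/30 with N20 is biased. Items 6 and 7 remove the whole recording from both, so the comparison stays paired. A difference in readability between the two potentials is only a possibility, on which the plan is silent.
- That section 7.7 contradicts section 4.5. It can be read as covering eligible patients who were not withdrawn; the two are unreconciled.

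**What to change.** - Remove items 6 and 7 of section 4.5 as reasons for withdrawal, and keep these patients in follow-up to hospital discharge.
- Report technical failures and uninterpretable recordings separately, by CPC outcome (1–2 versus 3–5) and for each of N20 and P25/30.
- Keep the readable-only accuracy, labelled as such. Pre-specify beside it an all-recorded analysis of sensitivity, specificity, PPV and NPV under both bounds: unreadable as not positive, and unreadable as positive.
- Reconcile sections 4.5, 7.5 and 7.7 so that they describe one analysis set, with the readable-only set as a named subset.

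This needs no new test, no extra staff and no change in care. Section 7.6 already allows a separate SAP before the study is completed. The cost is some wording, one extra table, and an all-recorded sensitivity that will look less favourable under the not-positive bound if any poor-outcome recording fails.
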